9.2 Dosage Information

Liraglutide doses will be self-administered by the participant through daily subcutaneous injections. Liraglutide dose will be initiated at 0.6 mg and then increased to 1.2mg in week two, 1.8mg in week three, 2.4mg in week four and 3.0mg in week five. The dose will then be maintained at 3.0mg. A slow escalation of the LIRA 3mg dose should help reduce the dropout of participants due to side effects. Where LIRA 3mg doses are not tolerated by the participant they will be withdrawn from the treatment condition.

9.3 Storage of Study Treatment

Study medication will be stored in a refrigerator at 2 – 8 °c. It will not be frozen. Participants in the LIRA 3mg treatment group will be instructed to store the drug away from the freezer compartment and to store below 30°C or store in a refrigerator (2°C - 8°C) after first use. They will also be instructed to keep the cap on the pen in order to protect from light.

The employment, dosing, handling, storage and destruction of LIRA 3mg will be conducted in accordance with the specified conditions of its approved labelling and in-line with pharmacy protocols and guidelines.

The Co-PI or delegated individual/personnel in each site or other personnel allowed to store and dispense the investigational medication will be responsible for ensuring that the investigational drug is securely maintained as specified by the Sponsor and in accordance with applicable regulatory requirements. It is the co-PIs (or other delegated personnel's) responsibility to ensure that an accurate record of investigational medications issued will be maintained.

Any quality issue noticed with the receipt or use of an investigational medication (deficiency in appearance, pertaining documentation, labelling, expiration date) should be promptly reported to the Sponsor. Some deficiencies may be recorded through a complaint procedure.

A potential defect in the quality of the investigational medication may be subject to initiation of a recall procedure by the Sponsor. In this case, the co-PIs will be responsible for promptly addressing any request made by the Sponsor, in order to recall investigational medication and eliminate potential hazards.

Under no circumstances will the PIs supply investigational medication to a third party, allow the investigational drug to be used other than as directed by this clinical study protocol, or dispose of investigational device(s) in any other manner other than that directed by pharmacy.

9.4 Compliance with Study Treatment

All participants in the study who have been prescribed LIRA 3mg should administer the drug daily. The participants will be instructed to return all unused, used or part-used medication/vials and packaging from used medication at each visit. Adherence questions will also be asked in follow-up visits for participants on LIRA 3mg. Examining medication returns and evaluating adherence will allow for an assessment of compliance and drug accountability. All participants should report all events which they believe may have impact on dose adjustment (such as nausea, vomiting). The Investigator may withdraw the participants if they consider dose compliance is unsatisfactory. Participants will be defined as treatment compliant if they take 70% of planned doses.

9.5 Accountability of the Study Treatment

The study medication will be supplied by Novo Nordisk to the host pharmacy. The employment, dosing, handling, storage and destruction of study medication will be conducted in accordance with the specified conditions of its approved labelling and in-line with local pharmacy guidelines.

Drug accountability will be the responsibility of the host pharmacy and will be fully documented.

The participant will be asked to bring all used, part-used and unused medication and used vials/packaging back to the clinic at each visit where it will be returned to pharmacy.

9.6 Concomitant Medication

Participants are allowed to continue the use of concomitant medication, which will be recorded in the CRF. However, consideration will be given also to reducing polypharmacy especially where participants have achieved significant weight loss and improvements in obesity related comorbidities. If concomitant treatment has to be changed during the study period, this must be reported on the CRF provided (trade name and/or generic name) and in the participant's medical records. If any changes in glucose, lipid and blood pressure lowering therapy is required (e.g. due to disease progression or improvement) during the study, this must also be documented on the CRF. Addition of any medication that will significantly influence weight, such as corticosteroids is reason for discontinuation of the participant in the treatment.

10. SAFETY REPORTING

10.1 Definitions

The reference safety information (RSI) for this study will be the Summary of Product Characteristics (SmPC).

10.1.1 Adverse Event (AE)

An AE or adverse experience is:

Any untoward medical occurrence in a patient or clinical investigation participants administered a medicinal product, which does not necessarily have to have a causal relationship with this treatment (the study medication).

An AE can therefore be any unfavourable and unintended sign (including an abnormal laboratory finding), symptom or disease temporally associated with the use of the study medication, whether or not considered related to the study medication.

10.1.2 Adverse Reaction (AR)

All untoward and unintended responses to a medicinal product related to any dose administered. The phrase "responses to a medicinal product" means that a causal relationship between a study medication and an AE is at least a reasonable possibility, i.e., the relationship cannot be ruled out. All cases judged by either the reporting medically qualified professional or the Sponsor as having a reasonable suspected causal relationship to the study medication qualify as adverse reactions.

10.1.3 Severe Adverse Events (SAE)

To ensure no confusion or misunderstanding of the difference between the terms "serious" and "severe", which are not synonymous, the following note of clarification is provided:

The term "severe" is often used to describe the intensity (severity) of a specific event (as in mild, moderate, or severe myocardial infarction); the event itself, however, may be of relatively minor medical significance (such as severe headache). This is not the same as "serious," which is based on patient/event outcome or action criteria usually associated with events that pose a threat to a participant's life or functioning. Seriousness (not severity) serves as a guide for defining regulatory reporting obligations.

10.1.4 Serious Adverse Event (SAE) or Serious Adverse Reaction (SAR)

Is an AE, AR, or other untoward serious medical occurrence or effect that:

- Results in death,
- Is life-threatening*,
- Requires inpatient hospitalisation or prolongation of existing hospitalisation**,
- Results in persistent or significant disability/incapacity, or
- Is a congenital anomaly/birth defect.
- Is otherwise considered medically significant by the investigator****

* "Life-threatening" in the definition of "serious" refers to an event in which the participant was at risk of death at the time of the event; it does not refer to an event which hypothetically might have caused death if it were more severe.

**Hospitalisation is defined as an unplanned, overnight, formal inpatient admission, even if the hospitalisation is a precautionary measure for continued observation. Thus hospitalisation for protocol treatment, elective procedures (unless brought forward due to worsening symptoms) or for social reasons are not regarded as a SAE.

***Medical judgement should be exercised in deciding whether AE is serious in other situations. AEs that are not immediately life-threatening or do not result in death or hospitalisation but may jeopardise the participant or may require intervention to prevent one of the other outcomes listed in the SAE definition above, should be considered serious. Suspicion of transmission of infections agents must always be considered an SAE.

If a participant dies as the result of an SAE, any post-mortem findings including histopathology must be provided.

10.1.5 Suspected Unexpected Serious Adverse Reactions (SUSAR)

A serious adverse reaction, the nature or severity of which is not consistent with the applicable product information Summary of Product Characteristics for LIRA 3mg (Saxenda).

Event Grade:

- Mild: Participant is aware of the event or symptom, but the event or symptom is easily tolerated.
- Moderate: Participant experiences sufficient discomfort to interfere with or reduce their usual level of activity.
- Severe: Significant impairment of functioning, participant is unable to carry out usual activities and/or the participant's life is at risk from the event.

After this initial evaluation the relationship of the AE to the study therapy/investigation medical therapy (IMP) will be assessed using the following definitions:

Definitely:

- The AE starts a reasonable time after the study therapy/IMP administration.
- The AE stops/ improves when the study therapy/IMP has been stopped.
- The AE can reasonably be explained by known characteristics of the study therapy/IMP.

Probably:

- A causal relationship is clinically/biologically highly plausible.
- There is a plausible time sequence between onset of the AE and administration of the study therapy/IMP.
- There is a reasonable response on withdrawal of the study therapy/IMP.
- It cannot be reasonably explained by known characteristics of the participant's clinical state.

Possibly:

- A causal relationship is clinically/biologically plausible.
- There is a plausible time sequence between onset of the AE and administration of the study therapy/IMP, however
- The AE could have been produced by the participant's clinical state or other modes of therapy administered to the patient.

Unlikely to be related:

- The time association or the participant's clinical state is such that the study therapy/IMP is not likely to have had an association with the observed effect.
- Another documented cause of the AE is most plausible.

Unrelated:

- The AE is definitely not associated with the study therapy administered.
- Another documented cause of the AE is most plausible.

10.2 Assessment periods

All Adverse events (AEs) will be recorded throughout the study whether serious or not. Members of the research team will ask the participants about AEs at each study time point (see Appendix 3) and will complete the participant AE form, which will be a continuous log so as to capture end dates, and the study serious adverse event (SAE) log. This will be evaluated and classed according to the definitions in section 10.3 below (European Directive 2001/20/EC).

10.3 Expected Serious Adverse Events/Reactions

Rare side-effects (less than 1%) will be reported as SAEs. The expected adverse events of renal impairment, cholecystitis and cholelithiasis will be reported as SAEs due to being medically significant.

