10.5 Reporting Procedures for All Adverse Events

All pregnancies, AEs, ARs, UARs, SAEs or SARs occurring during the study observed by the investigator or reported by the participant, whether or not attributed to study medication, will be recorded on the CRF and the medical notes. They will be reported in accordance with the Sponsor, host organisation, Novo Nordisk procedures, policies and requirements.

The following information will be recorded: description, date of onset and end date, severity, assessment of relatedness to study medication, other suspect drug or device and action taken. Follow-up information should be provided as necessary.

AEs considered related to the study medication as judged by a medically qualified investigator or the Sponsor will be followed until resolution or the event is considered stable. All related AEs that result in a participant's withdrawal from the study or are present at the end of the study, should be followed up until a satisfactory resolution occurs.

It will be left to the investigator's clinical judgment whether or not an AE is of sufficient severity to require the participant's removal from treatment (see section 10.1 and 10.2). A participant may also voluntarily withdraw from treatment due to what he or she perceives as an intolerable AE. If either of these occurs, the participant must undergo an end of study assessment and be given appropriate care under medical supervision until symptoms cease or the condition becomes stable.

The severity of events will be assessed on the following scale: 1 = mild, 2 = moderate, 3 = severe.

The relationship of AEs to the study medication will be assessed by a medically qualified investigator.

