Overall hypoglycaemia rate – ADA definition	52, 104	Hypoglycaemia events will be defined as per Appendix 5 for people without

		diabetes and as per the ADA definition in Appendix 5 for people with diabetes. Hypoglycaemia rate will be calculated per participant as total number of hypoglycaemia events divided by the total follow-up time.
Overall hypoglycaemia rate – Novo Nordisk	52, 104	Hypoglycaemia events will be defined as per Appendix 5 for people without diabetes and as per the Novo Nordisk definition in Appendix 5 for people with diabetes. Hypoglycaemia rate will be calculated per participant as total number of hypoglycaemia events divided by the total follow-up time.
AEs	Continual	Defined as in protocol with MEDRA coding used to classify AEs into System Organ Classes
SAEs	52, 104	Defined as in protocol with MEDRA coding used to classify SAEs into System Organ Classes
Rates of severe hypoglycaemia	52, 104	Calculated per participant as total number of severe hypoglycaemia events divided by the total follow-up time, where severe hypoglycaemia is defined as hypoglycaemic episodes requiring the assistance of another person to actively administer carbohydrate, glucagon, or other resuscitative actions (i.e., 'severe hypoglycaemic episodes')
Change in heart rate from baseline (beats per minute)	52, 104	Follow-up heart rate – baseline heart rate
Compliance of patient with the treatment		
Compliant with Tier 3 service (completers)	52, 104	Binary indicator of 1 if participant is compliant, 0 otherwise (defined in study database)
Stopped treatment with LIRA 3mg because of adverse effects	52, 104	Binary indicator of 1 if participant stopped treatment with LIRA 3mg because of adverse effects*, 0 otherwise. Only defined for participants in intervention arm who were currently eligible for LIRA 3mg treatment. * This includes main reason of 'adverse event' or 'unable to tolerate drug'.
The adherence of participants with the LIRA	52, 104	Participants will be defined as treatment compliant if they self-administer at least 70% of planned doses. Binary indicator of 1 if participant is compliant, 0 otherwise.

3mg (monitored through specific questionnaire and return of used pens)		Given the change in visits as a result of COVID-19 to allow face-to-face, this will be defined using the questionnaire answers as detailed in Appendix 7. Only defined for participants in intervention arm who were currently eligible for LIRA 3mg treatment.

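### Protocol 10.3 makes side-effects below 1% SAEs with no seriousness condition, against 10.1.4, and the SAP does not say which definition its SAE tables use

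*Protocol*

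**What the plan says.** Protocol 10.1.3 separates severity from seriousness and states: "Seriousness (not severity) serves as a guide for defining regulatory reporting obligations". Section 10.1.4 then defines an SAE by death, threat to life, unplanned inpatient admission, lasting disability or congenital anomaly. It adds one judgement-based criterion: "Is otherwise considered medically significant by the investigator". How common a reaction is plays no part.

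Protocol 10.3 has two sentences. The first is "Rare side-effects (less than 1%) will be reported as SAEs". The second is "The expected adverse events of renal impairment, cholecystitis and cholelithiasis will be reported as SAEs due to being medically significant". The second gives a reason that fits 10.1.4; the first gives none.

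Protocol 10.2, on the recording of AEs and SAEs, says: "This will be evaluated and classed according to the definitions in section 10.3 below".

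The SAP (section 2.2.1, SAEs row) reads: "Defined as in protocol with MEDRA coding used to classify SAEs into System Organ Classes". It does not say whether 10.1.4 or 10.3 decides.

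**The concern.** Frequency is not seriousness. Under the first sentence of 10.3, a mild, self-limiting but uncommon reaction is an SAE; under 10.1.4 it is not. A site that works from 10.1.4 and a site that works from 10.3 would classify the same event differently, and the SAP does not settle the matter at analysis.

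The overall AE/SAE rate is a listed safety outcome (Protocol 6.4.2). If the SAE tables mix serious and non-serious events, true serious events are harder to see, and a difference between arms may partly reflect classification. Allocation is open, so whether an event is called a side-effect of the study drug can depend on the arm. That gives the problem a possible direction.

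**Working it through.** The documents give no SAE figure to reproduce. The check is mainly a comparison of passages, followed by an illustration on stated assumptions.

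**Step 1. The two rules side by side**

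| | Protocol 10.1.3 and 10.1.4 | Protocol 10.3, first sentence |
|---|---|---|
| Basis for calling an event an SAE | Outcome, or medical significance judged by the investigator | Frequency below 1% |
| Judged for | The individual event | A type of side-effect |
| Seriousness needed? | Yes | Not stated |
| Drug or arm named? | No | No |

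An uncommon event that meets no 10.1.4 criterion is an AE under the first rule and an SAE under the second. The protocol does not list which side-effects fall below 1%. Section 10.1 names the SmPC as reference safety information, but 10.3 does not say that its frequencies are the ones to use.

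**Step 2. The route into the results**

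- Protocol 10.2 sends classification to 10.3.
- SAP 2.2.1 takes the SAE definition from the protocol, with no section named.
- That definition feeds the overall SAE rates by arm (SAP 16.13) and the SAE tables by System Organ Class and by expected type, with incidence rate ratios (SAP 16.15).
- The SAE listing in SAP section 6 names relatedness, expectedness, duration, severity, action taken, outcome and treatment. It does not name the seriousness criterion that was met.

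**Step 3. Does the rule act in one arm or both?**

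The word side-effect, with the SmPC of the study drug as reference, points to drug reactions and so to participants exposed to LIRA. Three things point to both arms:

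- The 10.3 heading covers events as well as reactions.
- Protocol 10.5 says that AEs and SAEs, "whether or not attributed to study medication, will be recorded on the CRF and the medical notes".
- SAP 16.15 has a Standard column for expected SAE types.

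The documents do not settle the question.

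**Step 4. Illustration**

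From the documents: 261 participants in the LIRA arm (Protocol 11.2). Assumed, because the documents do not say:

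- k side-effect terms below 1%, each occurring at rate q per participant (1% is the ceiling);
- every such event non-serious;
- b true SAEs per participant, equal in both arms, with equal follow-up.

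Formulas:

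- Extra events in the LIRA arm = 261 × k × q
- SAE ratio if only the LIRA arm is affected = (b + kq) / b
- SAE ratio if both arms are affected and control has half the rate = (b + kq) / (b + kq/2)

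| k × q | Extra LIRA-arm events | LIRA arm only, b = 5% | LIRA arm only, b = 10% | Both arms, control half, b = 5% | Both arms, control half, b = 10% |
|---|---|---|---|---|---|
| 1 × 0.5% = 0.5% | 1.3 | 1.10 | 1.05 | 1.05 | 1.02 |
| 5 × 0.5% = 2.5% | 6.5 | 1.50 | 1.25 | 1.20 | 1.11 |
| 10 × 1% = 10% | 26.1 | 3.00 | 2.00 | 1.50 | 1.33 |

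For example, with 5 terms at 0.5% and b = 5%: (0.05 + 0.025) / 0.05 = 1.50, and (0.05 + 0.025) / (0.05 + 0.0125) = 1.20. If the rule is applied by event type and the rates are equal in both arms, the ratio is 1.00 in every row. Using all 261 overstates exposure, because the stopping rules end LIRA for some participants at weeks 16, 32 and 52.

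**The case against.** The strongest reply is a narrower reading. Section 10.3 is headed as a section on expected serious events, and Protocol 14.10.1 speaks of rare serious adverse events such as hepatobiliary disease and pancreatitis. In that light, the sentence may mean only that rare serious effects are still reported as SAEs even though they are expected. The pointer in 10.2 may also be a wrong cross-reference, since the definitions stand in 10.1. This reading is possible, but it is not what the sentence says, and a site or analyst following the text would not reach it.

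A second reply is that over-reporting to the sponsor is cautious and that the SAE output is descriptive. Both are fair. A cautious reporting rule can stay, but the analysis still needs one definition of serious.

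A third is that the planned listings, with severity, relatedness and outcome, and the split by current LIRA use would expose a mild drug-related SAE. This stands in part: a careful reader could suspect such cases. The rates and ratios would still include them, and severity does not stand in for seriousness.

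A reader might go further and infer that the SAE comparison is inflated in the LIRA arm only, with no control affected. The documents do not support that. Section 10.3 names no drug or arm, and the SAP tabulates expected SAE types in both arms. Controls may also have side-effects of other anti-obesity drugs, which Protocol 8.3.2 has the sites ask about.

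**Conclusion.** The conflict is real: 10.3 as written makes non-serious events SAEs, 10.1.4 does not, and the SAP imports the protocol definition without choosing. The descriptive SAE rates, System Organ Class tables and incidence rate ratios can therefore include non-serious events.

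Upward bias in the LIRA arm is a risk, and the more plausible direction if a side-effect is taken to mean a reaction to the study drug. It is not an established result. The size cannot be computed: on the assumptions above the spurious ratio runs from 1.00 to 3.00, and only the arm size comes from the documents. No particular excess should be quoted as expected. The primary outcome is not touched and no hypothesis test is affected. The point is worth correcting because a stated safety outcome has two incompatible definitions and the correction is cheap.

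**What to change.** **SAP, before database lock.** The SAP supplied is a draft, version 1.1 of 01/08/2022, and its introduction says that it will be finalised before lock, so the change can still be made.

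- State that the SAE rates, System Organ Class tables, expected-type tables and rate ratios count an event only where a 10.1.4 criterion is met. Medical significance qualifies if it was judged for that event, not assigned only because the reaction is rare.
- State that the same rule applies in both arms.
- Keep renal impairment, cholecystitis and cholelithiasis as SAEs, as 10.3 provides.
- List separately, by arm, the reports that are SAEs only through the frequency rule.
- Add the seriousness criterion to the SAE listing.

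**Protocol.** Reconcile 10.2 and 10.3 with 10.1.4, or document the discrepancy. The amendment history gives a study end date of 30/06/2022, so a protocol change alone would probably come too late to alter what was collected. The SAP change does the work.

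**Cost.** The seriousness criterion must be checked on existing SAE reports. Protocol 10.5 does not list it among the recorded AE items and the SAE form is not among the documents, so a site query is needed wherever it was not recorded. Where medical significance is the only criterion given, the check must also establish whether it was judged for the event or followed from rarity. No safety information is lost, because the frequency-only reports stay visible in their own list.
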